#### Primary outcome:

Acute infection will be analyzed as a recurrent time-to-event using an Andersen-Gill Cox proportional hazards regression model with time since inclusion as underlying time scale.

The proportional hazards assumption will be tested using Schoenfeld residuals. The analysis

will be done for the composite outcome and for all the subcomponents separately presenting hazard ratio with 95% confidence intervals for each. Absolute risk reductions will be calculated using Cox regression.

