### Objectives and hypothesis

Primary objective: To reduce senior citizens' risk of acute infection during the COVID-19 pandemic.

Secondary objectives: To reduce senior citizens' risk of SARS-CoV-2 infection during the COVID-19 pandemic and to reduce self-reported respiratory illness in general during the COVID-19 pandemic.

The hypothesis is that BCG vaccination of seniors will reduce the risk of acute infection by 25% over a period of 12 months.

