### **Sample size**

With an expected incidence of “acute infection” of 20% we will be able to show a 25% reduction in the risk of acute infection in the intervention group compared to the placebo group by including a total of 1890 individuals: 945 individuals in each group. Since the primary outcome data to a large extent are obtained via national registers, we anticipate limited loss of power due to loss to follow-up. We therefore aimed to enroll 1900 participants.

Due to the pandemic and varying infectious disease precautions, recruitment took longer than anticipated, and we ended up recruiting a total of 1706 participants (90% of the anticipated sample size) between September 2020 and December 2021.

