## **4.0 STATISTICAL PRINCIPLES**

### **Levels of confidence and p-values**

A double-sided p-value of  $< 0.05$  will be considered statistically significant. 95% confidence intervals will be provided.

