### **Sample size**

We aim to include 75 participants in each group, 300 in total. With an anticipated seroconversion rate of 50% in the control group, we should be able to show a 30% increase in seroconversion rate associated with BCG vaccine with 80% power and an alpha of 0.05, anticipating 10% loss to follow-up.

All participants are followed for clinical symptoms for six months. With this sample size, we will only be able to show differences in clinical symptoms if such differences are pronounced.

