#### Secondary outcomes:

##### *Self-reported infections:*

The hazard ratio of infections will be estimated using an Andersen-Gill Cox proportional hazards regression model with infections included as recurrent events and time since inclusion as underlying time scale. The proportional hazards assumption will be tested using Schoenfeld residuals. As participants are only able to report one infectious episode during a follow-up questionnaire, the event will be assigned to the first day within the questionnaire period, and the following 14 days of follow-up excluded for analyses as it represents risk free time.

Association between influenza antibody titer level at day 42 and rate of infections will also be explored in Andersen-Gill Cox proportional hazards regression model, using antibody titer at day 42 as exposure and self-reported infections after day 42 as outcome. Antibody titers will be categorized into quartiles or similar relevant categories. The analysis will be adjusted for sex and age group.

Absolute risk reduction will be calculated using Cox regression.

*Immunological outcomes (subgroup analyses):*

Mean change in number of activated B-cells, concentration of cytokines, as well as fold change in cytokine concentration after stimulation from day 0 to day 14 and from day 14 to day 42 will be compared between the control group and the three treatment groups in linear regression analyses. With and without adjustment for responses in the control condition.

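### The absolute risk reduction for the recurrent infection outcomes has no fixed estimator; taken from the only Cox model named for them, Andersen-Gill, it is not a first-event risk

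*SAP*

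**What the plan says.** The Part A hypothesis is on the risk scale: BCG "will reduce the risk of acute infection by 25% over a period of 12 months". The sample size uses the same scale. It assumes an incidence "of 20% we will be able to show a 25% reduction in the risk of acute infection", and gets there "by including a total of 1890 individuals: 945 individuals in each group". The variables table in SAP Section 6.0 codes acute infection as binary.

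The analysis is on another scale. SAP Section 7.0, Primary outcome, fits acute infection and each subcomponent as recurrent events in an Andersen-Gill model, and the paragraph ends: "Absolute risk reductions will be calculated using Cox regression". Under Secondary outcomes, self-reported respiratory infection follows the primary-outcome method. A standard Cox model is named only for verified SARS-CoV-2 infection and all-cause hospitalization, both defined as first events.

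Part B has the same pattern. Section 14.0 describes two Andersen-Gill analyses of self-reported infection, names no other Cox model, and adds: "Absolute risk reduction will be calculated using Cox regression".

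Table 2 and Table 3 of Part A, and Table 3 of Part B, have a column for the absolute risk reduction, in percent with a 95% confidence interval, alongside a count and percentage of participants.

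**The concern.** An Andersen-Gill model describes the rate at which events occur, counting repeat events in the same person. Its cumulative baseline hazard is a mean number of events per person. It does not give the probability of having at least one event unless something is assumed about how events are spread over persons. The usual conversion, 1 − exp(−cumulative hazard), assumes that recurrences are independent within a person.

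The 14-day periods removed after each event add a further gap: the hazard refers to time at risk, not to the full calendar period.

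A percentage printed beside the proportion infected will be read as the 12-month risk difference that the hypothesis is about. If it is derived from the recurrent-event fit, it is something else. If the source is left open, two analysts can follow the same sentence and report different figures from the same data, and the choice falls after the data are seen.

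**Working it through.** **1. The plan's own figure.** Inputs from the SAP: 20% in the control group, a 25% relative reduction (so 15% with BCG), and two-sided alpha 0.05. Power is not stated for Part A. I assume the value given in Part B, "with 80% power and an alpha of 0.05".

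- Two proportions without continuity correction: n = [1.960·√(2·0.175·0.825) + 0.8416·√(0.20·0.80 + 0.15·0.85)]² / 0.05² = 905.4, so 906 per group.
- With continuity correction: n/4·[1 + √(1 + 4/(n·0.05))]² = 944.9, so 945 per group and 1890 in total.

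This matches the SAP exactly. The design is therefore a comparison of two first-event proportions with a risk reduction of 5.0 points.

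**2. The same design put through the recurrent-event conversion.** The SAP gives no recurrence rate and no between-person variation, so the following is assumed. Each person has a constant rate multiplied by a gamma frailty with mean 1 and variance θ. L is the mean number of events per person in 12 months.

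- First-event risk: p = 1 − (1 + θL)^(−1/θ), so L = [(1 − p)^(−θ) − 1]/θ. For θ = 0, L = −ln(1 − p).
- Converted Andersen-Gill figure: 1 − exp(−L).

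Example with θ = 1: L = 1/0.80 − 1 = 0.2500 (placebo) and 1/0.85 − 1 = 0.1765 (BCG). The converted values are 0.2212 and 0.1618, a difference of 5.9 points. The true difference is 5.0.

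| θ (assumed) | L placebo | L BCG | Converted difference, points | Ratio to true 5.0 | Difference in mean events per 100 persons |
|---|---|---|---|---|---|
| 0 | 0.2231 | 0.1625 | 5.0 | 1.00 | 6.1 |
| 0.5 | 0.2361 | 0.1693 | 5.5 | 1.09 | 6.7 |
| 1 | 0.2500 | 0.1765 | 5.9 | 1.19 | 7.4 |
| 2 | 0.2812 | 0.1920 | 7.0 | 1.41 | 8.9 |
| 3 | 0.3177 | 0.2094 | 8.3 | 1.66 | 10.8 |

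**3. Effect of the 14-day gap.** A simulation of 400,000 persons per arm, with the gap either removed from or left in the time at risk, gives the following.

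| θ | Converted difference, points | First-event difference, points |
|---|---|---|
| 0 | 5.03 and 4.84 | 5.03 and 4.88 |
| 1 | 5.71 and 5.78 | 4.89 and 4.99 |
| 2 | 6.74 and 6.85 | 4.95 and 5.10 |

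The gap does not change the picture.

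**4. Is the direction fixed?** No.

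- If BCG lowers only the rate of the first event, later events occur at the placebo rate and there is no frailty, the conversion gives 4.6 points against a true 5.0.
- With a rate ratio of 0.75 and a placebo mean of 4 events per year, it gives e^(−3) − e^(−4) = 0.0498 − 0.0183, about 3.15 points. The true values are 4.9, 5.0 and 4.5 for θ = 0.5, 1 and 2. These settings imply placebo first-event risks of 89%, 80% and 67%, far from the SAP's 20%.

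**The case against.** The SAP does not expressly say that the percentage comes from the Andersen-Gill fit. It writes only of Cox regression, the outcome is coded as binary, and a first-event Cox fit would satisfy the wording. Nor does it prescribe the 1 − exp(−cumulative hazard) conversion. This stands, and it limits the point to what would follow if that route were taken. It does not settle the matter: no first-event fit is described for these outcomes, and the natural reading of the paragraph points to the model just named.

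A reader might infer that the plan will overstate the absolute benefit. The document does not support that as a flat statement. There is no bias if recurrences are independent, overstatement if infections cluster in the same people, and understatement in the settings of step 4. The SAP gives no recurrence data, so every frailty variance above is an assumption.

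A reader might also infer that the whole column is affected. It is not. Verified SARS-CoV-2 infection and all-cause hospitalization use first-event Cox models, and death due to infection cannot recur.

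Finally, the hazard ratio, the primary test and the sample size do not depend on this column. That is correct and bears on the weight of the point.

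**Conclusion.** The point holds in a limited form. For acute infection and its recurrent subcomponents (hospital contact, antibiotics, doctor-identified infection), for self-reported respiratory infection, and for the infections in Part B, the SAP does not fix how the absolute risk reduction is estimated. The only Cox model it names for them yields a rate and not a risk.

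If the percentage is taken from that model by the usual conversion, it is not the 12-month (Part B: six-month) risk difference unless recurrences are independent within persons. It would probably be too large, because clustering of infections in the same people is plausible. At the design risks the excess runs from 0 to 3.3 points on a true 5.0 for frailty variances from 0 to 3. That range rests on the assumed gamma frailty and constant rates.

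The hazard ratios stand. What needs repair is a prominent column of the main results tables.

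**What to change.** In Sections 7.0 and 14.0, for the recurrent outcomes:

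- Define the absolute risk reduction by randomised arm as the difference in first-event risk at 12 months (six months in Part B). Take it from a first-event Cox model or from a cumulative incidence estimate that treats death as a competing event (for the composite, death from causes other than infection). Give a bootstrap or robust 95% interval, clustered on couples in Part A.
- Label any absolute quantity from the Andersen-Gill fit as a difference in mean number of events per person, or per 100 persons, over follow-up.
- For the rows of Part A Table 3 before and after other vaccines, where status changes during follow-up, report a rate difference instead. A 12-month risk by arm is not defined there.
- For the antibody-quartile rows of Part B Table 3, which count infections only after day 42, state the horizon separately.

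The cost is a few sentences and one extra fit per recurrent outcome. One limit remains and should be stated: self-reported outcomes are observed only in completed questionnaire periods, so the first observed event may not be the participant's first event.

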#### **Secondary outcomes:**

The secondary endpoint self-reported respiratory infection will be analyzed the same way as the primary endpoint. As participants are only able to report one infectious episode during a follow-up questionnaire, the event will be assigned to the first day within the questionnaire period, and the following 14 days of follow-up excluded for analyses as it represents risk free time.

The secondary outcomes verified SARS-CoV-2 infection and all-cause hospitalization will be analyzed in a standard Cox proportional hazards model, but otherwise as described above.

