## 3.0 STUDY METHODS

### Trial design

A single-blinded, placebo controlled randomized clinical trial. Participants are randomized 1:1 to BCG or placebo and will be followed for 12 months post-randomization with respect to illness, medical contacts, use of antibiotics, hospitalization, and death. The follow-up takes place both through self-reporting and through the Danish National Registers. The participants will receive an electronic questionnaire biweekly with questions about illness, medical contacts, other vaccinations, and side effects.

People  $\geq 65$  years of age are eligible for participation.

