### **Randomization**

Randomization takes place at baseline after informed consent is given. The randomization is done in varying blocks of 6-8, stratified by sex and age group (65-74; 75+) using REDCap electronic data capture tools hosted at the Region of Southern Denmark.

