## 7.0 ANALYSIS

### Methods

All analyses will be performed from the intention-to-treat principle, for all participants studied together and stratified by sex and age group.

Several couples participated in this study. To consider shared vulnerability, we will cluster on couples (non-stratified analysis).

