### Exploratory analysis

Participants were enrolled during different stages of the COVID-19 pandemic. We will therefore conduct a subgroup analysis of all outcomes comparing participants included in the same phase of the pandemic. We will compare outcomes for participants included in the following periods:

1. September 2020 to January 2021 (N=1239); before the COVID-19 vaccines were widely distributed to the target population. A period characterized by increasing infection control measurements and concluding in lockdown.
2. April to December 2021 (N=438); Participants are now being vaccinated with the new coronavirus vaccines; most have had the two or three doses before enrollment. A period characterized by varying COVID-19 activity; a minimum of restrictions on society despite periodically high transmission rates (Omicron variant in the fall).

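### Stratifying the main Cox model for verified SARS-CoV-2 infection by month of enrolment would be a cheap gain in power; the planned single baseline hazard spans very different pandemic phases

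*SAP*

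**What the plan says.** Part A, section 7.0, Secondary outcomes, states that verified SARS-CoV-2 infection and all-cause hospitalization "will be analyzed in a standard Cox proportional hazards model, but otherwise as described above". The description above it is the primary-outcome model, fitted "with time since inclusion as underlying time scale". The Methods paragraph plans analyses "for all participants studied together and stratified by sex and age group" and clustering on couples. Neither calendar time nor enrolment date enters the main model.

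The Exploratory analysis section opens with "Participants were enrolled during different stages of the COVID-19 pandemic". It sets apart period 1 (September 2020 to January 2021, N=1239), which ended in lockdown, and period 2 (April to December 2021, N=438), with few restrictions, at times high transmission and mostly vaccinated enrollees. It plans a subgroup analysis of all outcomes by these periods, and Table 3 has rows for it.

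On design, the SAP says "Participants are randomized 1:1 to BCG or placebo", "The randomization is done in varying blocks of 6-8, stratified by sex and age group", and that participants "will be followed for 12 months post-randomization".

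**The concern.** For a pandemic infection, calendar time drives risk. On the time-since-inclusion scale, month 3 of an autumn 2020 enrollee and month 3 of an autumn 2021 enrollee fall in the same risk set, although their infection hazards may differ several-fold. If BCG protects, high-hazard participants leave the risk set faster in the placebo arm. The arms then drift apart in their mix of enrolment periods, and the pooled hazard ratio moves toward 1.

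Reducing SARS-CoV-2 infection is a named secondary objective, and recruitment reached 1706 of the 1900 aimed for (90%). Power that can be kept at no data cost is worth keeping. Enrolment date is known for everyone, but the plan uses it only for exploratory subgroups, which leave the pooled estimate as it is.

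**Working it through.** **The plan's own figure.** The only Part A sample size is for acute infection: 20% against 15%, 945 per group. Power is not stated there; 80% is assumed, as in Part B.

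- Without continuity correction: n = [1.96·√(2×0.175×0.825) + 0.842·√(0.20×0.80 + 0.15×0.85)]² / 0.05² ≈ 906.
- With it: (n/4)·[1 + √(1 + 4/(0.05n))]² ≈ 945, as stated.

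This says nothing about SARS-CoV-2 infection, for which the SAP gives no incidence, effect or power. The inputs below are therefore assumptions, apart from 1239, 438, the 12 months, the 1:1 allocation and the blocks of 6-8.

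**Mechanism, by hand.** Assume placebo risks of 10% (period 1) and 50% (period 2), and a true hazard ratio of 0.75 within each period.

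- Yearly hazards are -ln(0.90) = 0.105 and -ln(0.50) = 0.693. Starting shares are 1239/1677 = 0.739 and 438/1677 = 0.261.
- At entry the ratio of mean hazards is exactly 0.75.
- Placebo at 12 months: 0.739×0.90 = 0.665 and 0.261×0.50 = 0.131 are still at risk. The mean hazard is (0.665×0.105 + 0.131×0.693)/0.796 ≈ 0.2018.
- BCG at 12 months: survival is 0.90^0.75 = 0.924 and 0.50^0.75 = 0.595, so 0.683 and 0.155 are at risk. The mean hazard is (0.683×0.079 + 0.155×0.520)/0.838 ≈ 0.1607.
- The ratio at 12 months is 0.1607/0.2018 = 0.796.

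The pooled Cox estimate averages this drift from 0.75 to 0.796. Solving the expected score equation gives a large-sample value of 0.772. The same calculation gives 0.755 at 5%/20%, 0.765 at 6%/35% and 0.779 at 11%/58%.

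**Simulation.** 1239 + 438 participants, blocks of 6 and 8 within sex and age strata, 12 months, true hazard ratio 0.75, 2000-3000 runs per scenario where the number was recorded. Some runs held hazards constant within a period and others varied them by calendar date, so compare within rows, not between them.

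| Assumed 12-month risk, period 1 / 2 | Strata | HR, one baseline | HR, stratified | Power, one baseline | Power, stratified |
|---|---|---|---|---|---|
| 2% / 12% | month | 0.752 | 0.748 | 20% | 21% |
| 5% / 20% | period | 0.755 | 0.749 | 35% | 37% |
| 4% / 22% | month | 0.757 | 0.749 | 32% | 36% |
| 6% / 35% | period | 0.763 | 0.749 | 47% | 53% |
| 8% / 40% | month | 0.764 | 0.748 | 55% | 61% |
| 10% / 50% | period | 0.771 | 0.749 | 63% | 71% |
| 11% / 58% | period | 0.779 | 0.752 | 66% | 76% |

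Other month-stratified runs agree: power went from 54% to 59% at 7%/34% and from 72% to 82% at 14%/56%. At 9%/19% the gain was about 1 point or less. A steeper contrast costs more (48% against 61% at 5%/50%).

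**Standard error.** It is set mainly by the number of events. At 10%/50% about 307 events are expected, and 2/√307 = 0.114 against a simulated 0.115 with or without strata. At 6%/35% it is 0.143 either way; at 7%/34% it is 0.140 unstratified, by period and by month. The robust standard error agrees with the model one to within 0.001.

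**No true effect, 5%/50%.** Under blocked randomization the unstratified estimate is centred on 1.00. Its reported standard error is 0.120, its actual spread 0.101, and it rejects in 2.0% of runs. Stratified by period, the figures are 0.120, 0.118 and 4.2%. Under simple randomization the unstratified model reports 0.120 against 0.121 and rejects in 5.2%. The conservatism therefore comes from the blocks, which balance the arms over enrolment time without the unstratified model crediting it. Across the null scenarios examined, the unstratified model rejects in about 2-4.5%.

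Couples were not simulated.

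**The case against.** The strongest reply is that the plan is valid as it stands. The pooled hazard ratio is unbiased under the null, the false-positive rate stays below 5%, and a hazard ratio averaged over all enrollees is a legitimate summary. Preferring one conditional on enrolment time is a choice of estimand. This stands, and it is why the point is an improvement rather than an error.

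It can also be said that the size rests wholly on assumed risks. Most period 2 enrollees were already vaccinated, and 12-month follow-up carries many period 1 enrollees into autumn 2021 as well; both could narrow the contrast. This also stands. At low risks or with similar phases, the gain is a point or a few.

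The by-period rows in Table 3 answer the point only in part. They show within-period hazard ratios but split the data and leave the main estimate unchanged.

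A reader might infer that the planned interval is too wide and that stratifying would narrow it. The calculations do not support that. The reported standard error is the same with and without strata; it exceeds only the unstratified estimator's own spread under blocked randomization. Stratifying closes that gap by raising the spread. Power returns because the hazard ratio is no longer pulled toward 1.

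**Conclusion.** This is a cheap improvement. The main model for verified SARS-CoV-2 infection ignores a strong, fully known predictor of risk that the SAP itself describes. If BCG works, the pooled hazard ratio is attenuated relative to the within-period effect: a true 0.75 appears as roughly 0.75 to 0.78 over the range below. The power lost is about 1-4 points at low risks or similar phases, 5-6 points at about 6-7%/35%, and about 10 points at 11-14%/56-58%.

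These sizes assume a hazard ratio of 0.75, common to both periods, and infection risks that the SAP does not state. A reader might also infer bias or inflated type I error. Neither occurs: under the null the estimate is centred on 1 and the test is conservative. No gain has been shown for all-cause hospitalization or for the Andersen-Gill models.

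**What to change.** In Part A, section 7.0, Secondary outcomes, state that the main Cox model for verified SARS-CoV-2 infection has its baseline hazard stratified by calendar month of enrolment, with time since inclusion as the time scale and clustering on couples retained. Keep the unstratified model as a sensitivity analysis.

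Month is preferable to the two periods because 1239 + 438 = 1677, which is 1706 - 1677 = 29 short of the number recruited. The two periods also skip February and March 2021, and the SAP does not say where the 29 belong. Month strata place everyone by enrolment date. In the simulations, month and period strata gave practically the same gain.

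The cost is one strata term and one sentence, with no new data. The hazard ratio becomes conditional on enrolment month. The absolute risk reduction in Table 2, which the SAP takes from Cox regression, would have to be averaged over the month-specific baselines, and the text should say so. Using the same strata for all-cause hospitalization and the Andersen-Gill models is optional.
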